11.2 ADVERSE EVENT AND SERIOUS ADVERSE EVENT COLLECTION AND REPORTING

The investigator shall maintain and keep detailed records of all AEs in their patient files.

Collection of AEs

The study is a non-interventional study in real-world situation and will be conducted within the conditions of the approved marketing authorization. For this reason, the following AE collection and reporting requirements have been defined.

All adverse events occurred from the signing date on data release consent form to last visit date of monitoring period need to be collected, documented and reported to the sponsor using the AE page of eCRF(14.1).

The investigator carefully assesses whether an AE constitutes an ADR using the information below.

Causal relationship of adverse event

The definition of an adverse reaction implies at least a reasonable possibility of a causal relationship between a suspected medicinal product and an adverse event. An adverse reaction, in contrast to an adverse event, is characterized by the fact that a causal relationship between a medicinal product and an occurrence is suspected.

Medical judgment should be used to determine the relationship, considering all relevant factors, including pattern of reaction, temporal relationship, de-challenge or re-challenge, confounding factors such as concomitant medication, concomitant diseases and relevant history.

Arguments that may suggest a **reasonable causal relationship** could be:

- The event is **consistent with the known pharmacology** of the drug
- The event is known to be caused by or **attributed to the drug class**
- A **plausible time to onset of the event** relative to the time of drug exposure
- Evidence that the **event is reproducible** when the drug is re-introduced
- **No medically sound alternative etiologies** that could explain the event (e.g. preexisting or concomitant diseases, or co-medications).
- The event is typically **drug-related and infrequent in the general population** not exposed to drugs (e.g. Stevens-Johnson syndrome).
- An indication of dose-response (i.e. greater effect size if the dose is increased, smaller effect size if dose is diminished).

Arguments that may suggest that there is **no reasonable possibility of a causal relationship** could be:

- No plausible time to onset of the event relative to the time of drug exposure is evident (e.g. pre-treatment cases, diagnosis of cancer or chronic disease within days/weeks of drug administration; an allergic reaction weeks after discontinuation of the drug concerned)

- Continuation of the event despite the withdrawal of the medication, taking into account the pharmacological properties of the compound (e.g. after 5 half-lives). Of note, this criterion may not be applicable to events whose time course is prolonged despite removing the original trigger.
- Additional arguments amongst those stated before, like alternative explanation (e.g. situations where other drugs or underlying diseases appear to provide a more likely explanation for the observed event than the drug concerned).
- Disappearance of the event even though the study drug treatment continues or remains unchanged.

The causal relationship must be provided by the Investigator for all potential study drugs, i.e. the BI study drug and for all other study drugs.

The reason for the decision on causal relationship needs to be provided in the eCRF and on the NIS AE form (if applicable).

Related

- Certain : An event occurring in a plausible time relationship to drug administration and that cannot be explained by concurrent disease or other drugs or chemicals. The response to withdrawal of the drug (dechallenge) should be clinically plausible. The event must be definitive pharmacologically or phenomenologically, using a satisfactory rechallenge procedure if necessary.
- Probable/Likely : An event with a reasonable time sequence to administration of the drug, unlikely to be attributed to concurrent disease or other drugs or chemicals, and which follows a clinically reasonable response on withdrawal (dechallenge). Rechallenge information is not required to fulfill this definition.
- Possible: An event with a reasonable time sequence to administration of the drug, but which could also be explained by concurrent disease or other drugs or chemicals. Information on drug withdrawal may be lacking or unclear.
- Conditional/Unclassified: Case of requiring more data or reviewing the additional data for the appropriate assessment
- Unassessable/Unclassifiable: Case that it cannot be judged and complemented or confirmed due to the insufficient or contradictory information

Unrelated

Unlikely : An event with a temporal relationship to drug administration which makes a causal relationship improbable, and in which other drugs, chemicals or underlying disease provide plausible explanations.

Intensity of adverse event

The intensity of the AE should be judged based on the following:

Mild: Awareness of sign(s) or symptom(s) which is/are easily tolerated

Moderate: Enough discomfort to cause interference with usual activity

Severe: Incapacitating or causing inability to work or to perform usual activities

Boehringer-Ingelheim
Non-interventional Study Protocol
BI Study Number 1275-0028

c37168579-01

Proprietary confidential information © 2022 Boehringer Ingelheim International GmbH or one or more of its affiliated companies

Expedited Reporting of AEs and Drug Exposure during Pregnancy to BI Pharmacovigilance

The following must be reported by the investigator on the NIS AE form and/or Pregnancy Monitoring Form(14.3) from signing the data release consent onwards until the end of the study and provide to the LPVM of [REDACTED]

Contact details:

Local PV Manager (LPVM)

Tel: [REDACTED]

Fax: [REDACTED]

Address: [REDACTED]
[REDACTED]

Type of Report	Timeline
All Serious Adverse Events (SAEs)	immediately within 24 hours
All AEs with fatal outcome	immediately within 24 hours
All protocol specified Adverse Event of Special Interest (AESIs)	Immediately within 24 hours
All non-serious adverse events	7 calendar days
Drug exposure during pregnancy	7 calendar days

The same timelines apply if follow-up information becomes available for the respective events. In specific occasions the Investigator could inform the Sponsor upfront via telephone. This does not replace the requirement to complete the AE page of the eCRF and/or the NIS AE form.

Pregnancy:

In rare cases, pregnancy might occur in a NIS. Once a patient has been enrolled in the study and has taken study medication, the investigator must report any drug exposure during pregnancy in a study participant within 7 days by means of Part A of the Pregnancy Monitoring Form (14.3) to the LPVM of [REDACTED]

The outcome of the pregnancy associated with the drug exposure during pregnancy must be followed up and reported to the LPVM of [REDACTED] on the Pregnancy Monitoring Form (Part B).

The ISF will contain the Pregnancy Monitoring Form (Part A and B). As pregnancy itself is not to be reported as an AE, in the absence of an accompanying serious ADR and/or AESI, only the Pregnancy Monitoring Form and not the NIS AE form is to be completed. If there is a serious ADR and/or AESI associated with the pregnancy a NIS AE form must be completed in addition.

Information required

Boehringer-Ingelheim**Non-interventional Study Protocol****BI Study Number 1275-0028****c37168579-01**

Proprietary confidential information © 2022 Boehringer Ingelheim International GmbH or one or more of its affiliated companies

For each reportable adverse event, the investigator should provide the information requested on the appropriate eCRF page and the NIS AE form.

For each AE, the investigator will provide the onset, end, intensity, outcome, seriousness and action taken with Esglito. The investigator will determine the relationship of Esglito to all AEs as defined in the 'Adverse Event Reporting' section of the investigator binder.

Reporting of related AEs associated with any other BI drug

The investigator is encouraged to report all adverse events related to any BI drug other than Esglito according to the local regulatory requirements for spontaneous AE reporting at the investigator's discretion by using the locally established routes and AE report forms. The term AE includes drug exposure during pregnancy, and, regardless of whether an AE occurred or not, any abuse, off-label use, misuse, medication error, occupational exposure, lack of effect, and unexpected benefit.

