9.7.2 Analysis of Safety

- ① Among the subjects of safety evaluation, the number of subjects with adverse event incurred and the number of adverse events incurred should be calculated, and the frequency of adverse events and the 95% confidence interval should be presented.
- ② The number and percentage of adverse events by type and category should be presented.
- ③ Analysis should be made using Chi-square test or Fisher's Exact test on the adverse event onset status by demographic data of subjects of safety evaluation.
- ④ To estimate any factors that are thought to influence the analyzed frequency of adverse events, logistic regression analysis should be conducted, and for statistically significant parameters, the meaning should be described.

Adverse Events (AEs) excluding the AEs whose 'Causality' is "Unlikely" will be treated as AEs whose causality cannot be excluded (hereafter "Adverse Drug Reaction (ADR)").

AEs will be coded according to the latest version of Medical Dictionary for Drug Regulatory Affairs (MedDRA) coding system. Concomitant medications will be coded according to the latest version of KIMS(Korea Index of Medical Specialties) coding system. The study database will not be locked until coding is complete.

Safety analyses will be based on all patients treated, i.e. all patients who received at least one dose of Esgliteo. However, if data for patients who have been treated with Esgliteo beyond the scope of approved label are collected, separate safety analyses will be performed. Patients lost to follow up will be characterized compared to the remaining patients and reason and time point of loss to follow up will be evaluated.

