6.2 HANDLING OF MISSING DATES

If there are missing dates which are needed in calculations, they will be imputed as described in the following.

If date of last safety assessment is missing when processing missing values on end date of administration of Esgliteo, it is replaced with date of last visit.

Table 2 Handling of missing dates

Types of Dates	Missing	Imputation	Examples
Diagnosed date	DD	01	Collected date: 2021-12-UK Imputed date: 2021-12-01
End date of Esgliteo administration	DD	1. [Year-Month] is the same as date of last safety assessment [Year-Month]: date of last safety assessment [Day] 2. [Year-Month] is different from date of last safety assessment [Year-Month]: 31	1. Date of last safety assessment: 2021-12-21 Collected date: 2021-12-UK Imputed date: 2021-12-21 2. Date of last safety assessment: 2021-12-21 Collected date: 2021-11-UK Imputed date: 2021-11-31
Start date of other anti-diabetic agent/	MM-DD	01-01	Collected date: 2021-UK-UK Imputed date: 2021-01-01
Prior/concomitant medications administration	DD	01	Collected date: 2021-12-UK Imputed date: 2021-12-01
End date of other anti-diabetic agent/	MM-DD	12-31	Collected date: 2021-UK-UK Imputed date: 2021-12-31
Prior/concomitant	DD	Last [day] of the month	Collected date: 2021-12-UK

CONFIDENTIAL

STATISTICAL ANALYSIS PLAN

Types of Dates	Missing	Imputation	Examples
medications			Imputed date: 2021-12-31
administration			

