6.3 HANDLING OF DERIVED VARIABLES

The baseline is considered to be the start date of the first administration of Esgliteo and the baseline value is defined as the last value measured before the first administration.

Derivation/imputation of variables will be performed as in the following.

Table 3 Derived variables

Variable	Derivation Method
Change from baseline	Post-baseline value – Baseline value
Age group	Less than 19 years 19 years or older and less than 30 years 30 years or older and less than 40 years 40 years or older and less than 50 years 50 years or older and less than 60 years 60 years or older
Duration of disease (years)	(Date of data release consent – Diagnosed date) / 365.25
Geriatric population	65 years or older, Less than 65 years
Total period of drug use(days)	End date of Esgliteo final administration – Start date of Esgliteo first administration+1 If [Continuing] is checked on CRF [DISPENSING OF ESLITEO] page, end date of Esgliteo final administration will be replaced with date of last safety assessment, and if date of last safety assessment is missing, it is replaced with date of last visit.
10/5mg, 25/5mg Sum of total period of drug use(days)	Sum of ((End date of Esgliteo administration - Start date of Esgliteo administration +1) per duration of visit) If [Continuing] is checked on CRF [DISPENSING OF ESLITEO] page, end date of Esgliteo final administration will be replaced with date of last safety assessment, and if date of last safety assessment is missing,

CONFIDENTIAL

STATISTICAL ANALYSIS PLAN

Variable	Derivation Method
	it is replaced with date of last visit.
Total number of administrations	Sum of (Administration frequency ^[1] ×period of drug use) per duration of visit [1] QD: Once a day, BID: Twice a day, TID: Three times a day, QID: Four times a day, PRN: Whenever necessary But, the value collected with PRN is excluded from analysis.
Average number of administrations per day	Total number of administrations / Total period of drug use
Duration of AE (Days)	AE end date – AE onset date +1 If [Continuing] is checked on CRF [ADVERSE EVENTS] page, AE end date will be replaced with date of last safety assessment, and if date of last safety assessment is missing, it is replaced with date of last visit, and will mark \geq (e.g. ≥ 15).
Onset duration of AE	AE onset date – Date of first Esglito administration
Less than 7% of HbA1c	yes: HbA1c $< 7\%$ no: HbA1c $\geq 7\%$

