8.1 SUMMARY OF ADVERSE EVENTS

The following types of AEs will be summarized with the number of subjects and proportion of the number of subjects with AE, number of cases and 95% exact confidence intervals.

- AE
- ADR
- SAE
- Serious adverse drug reaction (SADR)

CONFIDENTIAL

STATISTICAL ANALYSIS PLAN

- UAE
- Unexpected adverse drug reaction (UADR)
- Non-serious adverse drug reaction
- AESI
- Adverse events leading to discontinuation

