9.2 SECONDARY ENDPOINTS

- 1) The frequency, percentage and 95% confidence interval of the changes from baseline to 12 and 24 weeks will be summarized for patients who had HbA1c reaching less than 7% (target effectiveness response rate).
- 2) The frequency, percentage and 95% confidence interval of the changes from baseline to 12 and 24 weeks will be summarized for patients whose HbA1c was decreased by at least 0.5% at the last visit (relative effectiveness response rate).
- 3) For FPG, Weight, SBP and DBP, the changes from baseline to 12 and 24 weeks will be summarized using number of subjects, mean, SD, median, minimum, maximum, 5th percentile and 95th percentile, and will be compared using paired t-test.
- 4) Mean difference in the change of HbA1c from baseline to latest value according to following variables will be analyzed using t-test or ANOVA (Analysis of Variance).
 - Age group (Less than 19 years, 19 years or older and less than 30 years, 30 years or older and less than 40 years, 40 years or older and less than 50 years, 50 years or older and less than 60 years, 60 years or older)
 - Gender (Male, Female)
 - Height (<median, \geq median)
 - Weight (<median, \geq median)
 - Smoking status (Never smoked, Ex-smoked, Currently smokes)
 - Duration of disease (<median, \geq median)
 - Family history of T2DM (Yes, No)
 - Previous allergy (Yes, No)
 - Diabetes mellitus complications (Retinopathy, Neuropathy, Nephropathy, Vasculopathy, Other) (Yes, No, Not applicable)
 - Medical history (Yes, No)

CONFIDENTIAL

STATISTICAL ANALYSIS PLAN

- Comorbidities (Yes, No)
- Prior medication (Yes, No)
- Concomitant medication (Yes, No)
- Other anti-diabetic agent (Yes, No)
- Geriatric population (65 years or more, Less than 65 years)
- Pregnant women (Yes, No, Not applicable)
- Renal impairment (Yes, No)
- Hepatic impairment (Yes, No)
- Long-term use (24 weeks or more)
- Total period of drug use (<median, \geq median)
- Total number of administration (<median, \geq median)
- Average number of administration per day (<median, \geq median)
- Reasons for early interruption (Change to other antidiabetics, Consent withdrawal, Adverse events, Patient refusal to continue taking study medication, Follow up loss, Others)

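### The SAP sets no on-treatment window relative to the last Esgliteo dose, so AE, SAE, unexpected-AE and AESI proportions can include events that start after the drug was stopped

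*Protocol*

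**What the plan says.** **Collection.** Protocol 11.2: "All adverse events occurred from the signing date on data release consent form to last visit date of monitoring period need to be collected". The end of the window is a visit, not a dose.

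**Analysis population.** Protocol 9.7.2: "Safety analyses will be based on all patients treated, i.e. all patients who received at least one dose of Esgliteo". This defines who is counted. It does not limit when an event must start.

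**Counting.** SAP 8.1: "The following types of AEs will be summarized with the number of subjects and proportion of the number of subjects with AE", followed by a list that includes AE, SAE, unexpected AE (UAE) and AESI, with ADR, SADR and UADR in the same summary. SAP 8.2 repeats these types by system organ class and preferred term, and SAP 8.4 repeats the summary for subjects of special investigation. None has a condition on onset relative to the last dose.

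**Dates.** SAP 6.3, Table 3 derives onset as "AE onset date – Date of first Esglito administration". The same table uses "End date of Esgliteo final administration" for exposure, so the stop date is available, but nothing relates onset to it.

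**Stopping.** SAP 9.2 lists "Change to other antidiabetics" as one of six reasons for early interruption, without a frequency. SAP 6.2, Table 2 has an imputation rule for an Esgliteo end date falling in an earlier month than the last safety assessment: "Year-Month] is different from date of last safety assessment [Year-Month]: 31".

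**Causality.** Protocol 9.7.2 and SAP 8 treat every AE except those graded Unlikely as an ADR. Protocol 11.2 gives, as an example of implausible timing, "an allergic reaction weeks after discontinuation of the drug concerned".

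**The concern.** The primary objective is the safety profile of Esgliteo. Both documents define an AE as temporally associated with use of the product, and the protocol tells investigators that onset weeks after stopping argues against a causal link. The tables have no matching rule. An event that starts off drug but is recorded by the last visit enters the AE, SAE, UAE and AESI rows exactly as an on-drug event does, and the reader of the report cannot tell the two apart.

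The parallel ADR, SADR and UADR rows help only in part. They remove an off-drug event if the investigator grades it Unlikely. Conditional/Unclassified and Unassessable/Unclassifiable both stay in as ADRs, so a poorly documented late event can remain there too.

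The matter weighs most for rare AESIs, where one event changes the message, and for patients who stop early. It concerns events after the last dose only.

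**Working it through.** The plan has no figure to reproduce. The 600 patients are a regulatory requirement, and the documents give no AE rate, stopping rate or rule for follow-up after stopping. The check is therefore textual first, then a range under stated assumptions.

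**1. Can observation outlast dosing?** In the second worked example of SAP Table 2, the Esgliteo end date is November 2021 with the day unknown, and the last safety assessment is 21 December 2021. From 30 November (the month has no day 31) the gap is 21 days; from 1 November it is 50 days. The SAP thus foresees three to seven weeks between stopping and last assessment. SAP 4.4 also treats 24 weeks on drug and follow-up at 24 weeks as separate conditions.

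**2. How much could it matter?** Assumptions, not in the documents: constant AE hazard, the same on and off drug; 24-week risk 20%; a share d stops early at week s and is observed to week e; everyone else takes the drug to week 24.

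- Risk to week t = 1 − 0.8^(t/24). This gives 0.0365 at week 4, 0.0717 at week 8, 0.1056 at week 12 and 0.2000 at week 24.
- All collected = (1 − d) × 0.20 + d × risk(e).
- Onset on drug = (1 − d) × 0.20 + d × risk(s).
- Difference = d × [risk(e) − risk(s)].

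| d | s | e | All collected | On drug | Difference (points) | Share of AE patients with only off-drug events |
|---|---|---|---|---|---|---|
| 5% | 4 | 12 | 19.5% | 19.2% | 0.05 × (0.1056 − 0.0365) → 0.3 | 2% |
| 15% | 8 | 24 | 20.0% | 18.1% | 0.15 × (0.2000 − 0.0717) → 1.9 | 10% |
| 30% | 4 | 24 | 20.0% | 15.1% | 0.30 × (0.2000 − 0.0365) → 4.9 | 25% |

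If participation ends at stopping, e = s and the difference is zero.

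**3. Stopping spread over the study.** The last row above is near the extreme because everyone who stops does so at week 4. With stop times uniform over 24 weeks, the mean on-drug risk of those who stop is 1 − 0.20/0.2231 = 0.1037, where 0.2231 = −ln 0.8.

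- Followed to week 24: d × (0.2000 − 0.1037), which is 0.5 points at d = 5% and 2.9 points at d = 30%.
- Followed only to the next scheduled visit: d × [(0.1056 + 0.2000)/2 − 0.1037], which is 0.2 and 1.5 points.

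For scale, the exact 95% interval for 120/600 is 16.9% to 23.4%, a half-width of about 3.3 points.

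**4. Rare events.** One off-drug AESI in 600 gives 0.17% (exact 95% CI 0.004% to 0.93%), against 0% (upper limit 0.61%) without it.

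**5. Which on-treatment measure?** In the middle row of the table, the risk over 24 weeks of treatment is 20% by construction, yet the crude on-drug proportion is 18.1%: patients who stop stay in the denominator with shortened risk time. A rate avoids this. Expected patients with a first on-drug event are 600 × 0.18075 = 108.5. The constant hazard is 0.2231/24 = 0.0093 per week, so expected on-drug time to first event or stop is 108.45/0.0092976 = 11,664 patient-weeks. The rate is 108.45/11,664 × 52 × 100 = 48.3 per 100 patient-years, the same as the assumed hazard and unaffected by d or s.

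**The case against.** **Follow-up after stopping is not stated.** A reader might infer that patients who stop are routinely observed to week 24. The documents do not say so. SAP 7.4 ties reasons for early interruption to premature withdrawal from the study, Protocol 9.2.3.3 allows completion status and the final evaluation at Visit 2, and Protocol 9.2.3.5 describes further monitoring only for patients with AEs noted at the final visit or at discontinuation. This stands, and it is why the size cannot be fixed. It does not close the gap: Table 2 foresees a last assessment weeks after the end date, and no text ends AE collection at stopping.

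**The AE row does not attribute.** An AE is by definition not necessarily related. Attribution is carried by the ADR rows in the same summary, AEs are also tabulated by causality and by action taken, and SAEs are listed individually. This stands. The fault is that on-drug and off-drug events cannot be separated, not that the AE row claims causation.

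**An on-treatment proportion could be worse.** Under the constant-hazard model, the all-collected 20.0% is the right 24-week risk and 18.1% is too low. This stands against replacing the headline figures. It does not stand against showing the split beside them.

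**The model favours a large effect.** It takes stopping as unrelated to AEs, yet adverse events are a listed reason for stopping. Such patients are already counted, so a later event does not change the subject-level proportion. This stands, and it pulls the real excess down.

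**The long-term safety set already requires 24 weeks on drug.** True, so SAP 8.6 and 8.7 are largely unaffected. But that set is selected for staying on treatment and does not replace the main tables.

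**Conclusion.** The gap is real and lies in the SAP's counting rules, not in the protocol's collection rule. AE, SAE, UAE and AESI proportions can include events that start after Esgliteo was stopped, and only the ADR-type rows filter them, through the Unlikely grade alone.

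The size is unknown. It is near zero if participation ends at stopping. Under a 20% 24-week risk, equal hazard on and off drug, and 5% to 30% stopping early, it runs from about 0.3 to 4.9 points; the upper end needs 30% stopping at week 4 and all of them followed to week 24.

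Three stronger readings lack support. That patients who stop are often on another antidiabetic: switching is a listed reason with no frequency, so the most one can say is possibly. That the half-life remark in Protocol 11.2 supplies the window: it concerns an event continuing after withdrawal, not a new onset. That the headline proportions or the SAP 8.3 outcome should be replaced: for the proportions, the 18.1% against 20% comparison argues against it; in 8.3, total period of drug use is a predictor, and an on-treatment outcome would tie the opportunity for an event to that predictor.

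What remains is an inexpensive improvement that serves the primary objective directly.

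**What to change.** - **Leave unchanged:** AE collection, expedited reporting, the all-collected counts and the SAP 8.3 outcome. An on-treatment version of 8.3 is at most a sensitivity analysis.
- **State the follow-up:** say whether a patient who stops Esgliteo is observed to the next visit, to Visit 3, or not at all.
- **SAP 6.3:** add a flag for AE onset on treatment versus after stopping. On treatment means onset no later than the last Esgliteo end date plus a number of days that the sponsor fixes before the tables are produced. The flag needs a valid end date, and the Table 2 example produces 31 November, so that rule should use the last day of the month.
- **SAP 8.1, 8.2 and 8.4:** show AE, SAE, UAE and AESI split by the flag, beside the all-collected total.
- **On-treatment figure:** report it per on-drug person-time, for example per 100 patient-years, with any window days counted in the denominator as well.

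**Cost:** SAP wording, one flag from dates already collected, and one more column. The window length is a judgement and must be set in advance. SAP Section 1 already provides for recording a change of analysis and its reason in the final report.
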